5.5.6 Recommended treatment of adverse events

Medication used to treat AEs must be recorded on the Concomitant medications/Significant non-drug therapies eCRF.

5.5.7 Rescue medication

Not applicable.

5.5.8 Concomitant treatment

The Investigator should instruct the subject to notify the study site about any new medications he/she takes after the subject was enrolled into the study. All medications, procedures and significant non-drug therapies (including physical therapy and blood transfusions) administered after the subject was enrolled into the study will be recorded on the Concomitant Medications eCRF or the Surgical and Medical Procedures eCRF respectively.

CMV prophylaxis

Cytomegalovirus (CMV) prophylaxis, with i.v. ganciclovir or oral valganciclovir, will be used in patients (CMV positive and CMV negative) as per local medical practice. Prophylaxis should be recorded on the Concomitant Medications eCRF.

Pneumocystis jirovecii (Pneumocystis carinii) pneumonia (PCP) prophylaxis

All patients will be started on trimethoprim-sulfamethoxazole, starting when oral medication can be tolerated and continued throughout the study. The same regimen should be administered to all patients at a given study center. Aerosolized pentamidine or dapsone may be administered to patients unable to tolerate trimethoprim-sulfamethoxazole. Prophylaxis should be recorded on the Concomitant Medications eCRF.

Hepatitis B (HBV) prophylaxis

Prophylaxis for recurrent hepatitis B during the course of this study is allowed and will be administered at the discretion of the Investigator. Prophylaxis should be recorded on the Concomitant Medications eCRF.

BK virus

Patients with BK viremia or viruria should be treated according to local practice. If treatment is given it should be recorded on the Concomitant Medications eCRF.

Oral Candida treatment

For oral thrush (Candida), Nystatin may be used in a swish and swallow regimen; alternatively, clotrimazole (Mycelex®) lozenges/troches may be used. Routine use of systemic agents, e.g., itraconazole, voriconazole and fluconazole, will not be allowed in study Part 1 unless patients are systemically infected since azoles may increase blood concentrations of Tac. Systemic therapy in Part 2 is to be based on center practice and at the Investigator's discretion. Treatment should be recorded on the Concomitant Medications eCRF.

5.5.9 Prohibited treatment

Immunosuppressants other than those specified in the protocol are NOT allowed after informed consent up to the end of study. If the use of any of these medications or other non-protocol immunosuppressants is discovered prior to randomization/enrollment, the subject must not be randomized and will be recorded as a screen failure. If discovered after randomization/enrollment, no further doses are to be given, and the subject should continue on the randomized/assigned treatment regimen, noting the protocol deviation.

The exception is for the treatment of acute rejection not responding to corticosteroids.

5.5.10 Discontinuation of study treatment and premature subject withdrawal

Study “Stopping rules”

The following stopping rules based on potential toxicities will serve as the basis for placing the study on hold. Although the stopping criteria do not incorporate an absolute requirement for causality, the potential relationship between an AE and CFZ533 will be evaluated carefully on a case-by-case basis between the Sponsor and the Investigator. Following a review of the AE(s), a decision to permanently discontinue enrollment or re-initiate dosing will be made by the DMC.

- Two (2) or more patients presenting with PTLD or PML

In addition, specific stopping rules for the incidence of tBPAR will be applied. These rules are designed to ensure that a CFZ533 treatment arm will be stopped if there is high probability (>90%) that the true tBPAR rate is greater than 20%. Corporate Confidential Information

Corporate Confidential Information

In addition to the automatic hold criteria and tBPAR criteria presented above, the DMC will review safety data regularly as outlined in their charter (see [Section 8.4](#)) during quarterly and *ad hoc* meetings. The DMC can recommend stopping a specific study arm(s) or the entire trial if significant changes or effects that, in their collective opinion, are deemed unsafe or unethical to continue administering CFZ533.

Discontinuation of study regimen

The Dosage Administration Records for CFZ533 (all parts), MMF and Tac (Part 1 only) and Concomitant Medication eCRF for MMF and Tac (Part 2) will be used to record if a subject has permanently discontinued study treatment and why.

Possible reasons for study treatment discontinuation are:

- Adverse Event
- Lack of Efficacy
- Technical problem during transplant surgery
- Subject/Guardian Decision
- Lost to follow-up
- Death
- Graft Loss

The Investigator should discontinue a subject from their randomized treatment regimen if, on balance, he/she believes that continuation would be detrimental to the subject's well-being.

Subjects who become pregnant while taking study medication must be discontinued from study medication and from the study, such pregnancies should be reported as SAEs to Novartis DSE and entered as AEs in the eCRF, the reason for discontinuation of study medication should be recorded as AE and reason for discontinuation from study is pregnancy (see next section below).

Subjects who discontinue study medication (CFZ533 or Tac) should remain in the study, if possible, and receive standard of care immunosuppression, according to local practice, until completing the study at Month 6 (Part 1) or Month 12 (Part 2). Visits and assessments for such subjects are described in the [Assessment schedule](#). All immunosuppressants after discontinuation of study regimen must be recorded on the Concomitant Medication eCRF under the Immunosuppressive category.

Subjects who discontinue their study treatment regimen should NOT be considered withdrawn from the study UNLESS they withdraw their consent to participating in all the elements of the study (see [Section 5.5.11](#)). Information on treatment discontinuation needs to be captured on the end of treatment eCRF page. Such subjects should remain in the study, if possible, and receive standard of care immunosuppression, according to local practice, until completing the study at Month 6 (Part 1) or Month 12 (Part 2). See the [Assessment schedule](#) for the required assessments of these subjects after discontinuation of study regimen. If they fail to return for these assessments for unknown reasons, every effort should be made to contact them as specified in [Section 5.5.12](#).

5.5.11 Withdrawal of consent

Subjects may voluntarily withdraw consent to participate in the study for any reason at any time.

Withdrawal of consent occurs only when a subject does not want to participate in the study anymore and does not want any further visits or assessments and does not want any further study related contacts and does not allow analysis of already obtained biologic material.

If a subject withdraws consent, the Investigator must make every effort to determine the primary reason for this decision and record this information in the eCRF. Study treatment must be discontinued and no further assessments conducted. All biological material that has not been analyzed at the time of withdrawal must not be used. Further attempts to contact the subject are not allowed unless safety findings require communicating or follow-up.

5.5.12 Loss to follow-up

For subjects whose status is unclear because they fail to appear for study visits without stating an intention to withdraw, the Investigator should show "due diligence" by documenting in the source documents steps taken to contact the subject (e.g., dates of telephone calls, registered letters). A subject should not be considered lost to follow-up until his/her scheduled end of study visit would have occurred.

5.5.13 Replacement of early withdrawals or discontinuations

The sponsor allows for over-recruitment of 2 patients in Part 1 and additional 10% in Part 2, to compensate for potential early withdrawals or discontinuations from the study.

5.5.14 Emergency unblinding of treatment assignment

Not applicable.

5.5.15 Study completion and post-study treatment

Each subject will be required to complete the study in its entirety and thereafter no further study treatment will be made available to them (as applicable based on local regulations). Subjects who are prematurely withdrawn from the study should be treated according to local standard of care per Investigator's judgment. The study will complete when the last subject completes their Study Completion visit, and any repeat assessments associated with this visit have been documented and followed-up appropriately by the Investigator.

For Part 2: patients who completed the study on treatment with CFZ533 should be switched to

tacrolimus (or other SoC treatment) not earlier than 28 days after having received their last CFZ533 dose in order to not cause over-immunosuppression. From Days 28 to 35 after last dose, the concentration of tacrolimus should be at the lower recommended level before increasing it to the dose considered appropriate for the individual patient. Doses of MMF and CS may remain unchanged or be adapted accordingly.

5.5.16 Early study termination

The study can be terminated at any time for any reason by Novartis. Should this be necessary, the subject should be seen as soon as possible and treated as a prematurely withdrawn subject. The Investigator may be informed of additional procedures to be followed in order to ensure that adequate consideration is given to the protection of the subject's interests. The Investigator will be responsible for informing IRBs and/or ECs of the early termination of the trial.

6 Visit assessments

The full [Assessment schedule](#) is presented at the end of the synoptic section, above. "X" indicates assessments that are to be performed for all subjects. "A" indicates assessments only to be performed for subjects maintaining the study regimen.

All randomized subjects are expected to continue in the study up to Month 6 (Part 1) or Month 12 (Part 2) regardless of being on or off randomized treatment. Subjects who discontinue their randomized study treatment regimen should be treated according to standard of care immunosuppression and return for the assessments indicated by "X" in the [Assessment schedule](#). If they refuse to return for these assessments or are unable to do so, every effort should be made to contact them or a knowledgeable informant by telephone to determine the subject and graft status.

Subjects should be seen for all visits on the designated day with an allowed visit window as specified in the [Assessment schedule](#).

Every effort will be made to take the PK sample at the protocol specified time. Other assessments (e.g., ECG, vital signs) will be taken prior to or after the PK sample.

ECGs must be recorded after 5 minutes rest in the supine position to ensure a stable baseline. The preferred sequence of cardiovascular data collection during study visits is: ECG collection first, followed by vital signs, and blood sampling.

At a minimum, subjects will be contacted for safety evaluations (e.g., SAEs) up to 3 months after his/her last dose of CFZ533, and 2 months after End of Study visit (EoS) for patients in the control arm for Part 2. Documentation of attempts to contact the subject should be recorded in the source documentation.

6.1 Dietary, fluid and other restrictions

Not applicable.

6.2 Information to be collected on screening failures

All subjects who have signed informed consent but do not enter the next period (i.e., Randomized treatment to Month 6 or Month 12) will have the Study Completion eCRF for the screening period, demographics (giving reason for screen failure), inclusion/exclusion and SAE data collected. AEs that are not SAEs will be followed by the Investigator and collected only in the source data. All consented subjects must be entered in the IRT system at screening for Part 2. For subjects who are not randomized, the Screening Disposition eCRF must both be updated to indicate screen failure.

Rescreening is only allowed for subjects who were screen failures on the initial Screening visit (e.g., due to lab values out of range). Rescreened subjects should be recorded as screen failures under their original Subject ID number and assigned a new Subject ID number in the database when consented for rescreening.

All subjects who have signed informed consent and received study treatment will have all AEs **occurring after informed consent is signed** recorded on the Adverse Event eCRF until they completed the study.

Investigators will have the discretion to record abnormal test findings on the Medical History eCRF whenever in their judgment, the test abnormality occurred prior to the informed consent signature.

6.3 Subject demographics/other baseline characteristics

After informed consent has been signed and the subject's eligibility to participate in the study has been determined, baseline subject information will be obtained in accordance with local regulations, including date of birth, age, sex (with child bearing status for females), race and ethnicity. In addition, relevant medical history (including CKD and ESRD history) and current medical conditions at screening, a full physical examination, vital signs and a pregnancy test (for females of child-bearing potential) will also be performed.

At Baseline/Transplantation, information on the renal transplant procedure, recipient and donor transplant background, recipient and donor viral serology and recipient/donor HLA testing results will be recorded. For randomization/enrollment of subjects in Part 1, the sponsor must be contacted and the sponsor will assign the treatment number. For randomization of subjects in Part 2, the IRT must be contacted and the IRT will assign the randomization number. For all subjects regardless of randomization/enrollment status, the Enrollment (Part 1) or IRT (Part 2) and Screening Disposition eCRF must be completed to document all consented subjects as either randomized or as screen failures and the reason for screen failure recorded in the eCRF.

6.4 Treatment exposure and compliance

CFZ533 concentrations and PK parameters (measures of treatment exposure) will be determined in all subjects treated with study treatment, as detailed in [Section 6.7](#).

All pre-transplant immunosuppression administered pre-randomization/enrollment, such as basiliximab, Tac, MMF and/or CS, will be recorded on the Concomitant Medications eCRF under the Immunosuppressive category.

All post-randomization/enrollment doses of CFZ533 (all parts), Tac and MMF (Part 1 only) will be recorded on their respective Dose Administration Record eCRFs. For Part 2, Tac will be recorded on the Tac Concomitant Medications eCRF. Basiliximab (all parts), MMF (Part 2) and/or CS will be recorded on the Concomitant Medications eCRF under the Immunosuppressive category.

For all these immunosuppressive drugs, the start date, total dose, stop date and reason for dose administration or dose change are to be provided. If study drug is interrupted due to inability to tolerate oral medication and rescue therapy via a NG tube is administered, the non-study drug immunosuppressive should be recorded on the Concomitant Medications eCRF under the Immunosuppressive category.

Tac and MPA trough levels will be determined locally and recorded on the relevant trough level eCRF. The local trough values will be used to adjust the Tac and MPA dosing as needed. Post-discontinuation of study regimen, for patients remaining in study to Month 6 (Part 1) or Month 12 (Part 2), the trough levels should be recorded on the appropriate trough level eCRF.

Other drugs administered prior to and continuing at start of study medication will be entered on the Concomitant Medications eCRF.

Compliance will be assessed by the Investigator and/or study personnel at each visit and information provided by the patient. This information should be captured in the source document at each visit.

6.5 Efficacy / Pharmacodynamic assessments

6.5.1 Efficacy assessments

Treated Biopsy Proven Acute Rejection (tBPAR)

A treated BPAR is any condition where the subject received anti-rejection treatment and was histologically diagnosed as acute rejection (according to the Banff 2009 criteria, [Appendix 8](#) or the Banff 2013 criteria. Borderline histological findings are interpreted according to local medical practice and fulfill the criteria of tBPAR if anti-rejection treatment is given). Renal biopsies will be collected for all cases of suspected acute rejection.

Kidney allograft biopsy

For all suspected rejection episodes, regardless of initiation of anti-rejection treatment, an allograft biopsy must be performed according to local practice preferably within 48 hrs. Biopsies will be read by the local pathologist according to the updated Banff 2009 criteria ([Appendix 8](#), or the Banff 2013 criteria depending on the local practice). The results of the biopsy read by the local pathologist will be listed on the Kidney Allograft Biopsy eCRF. The results will be used for subject management for acute rejection. The local pathologist will remain blinded to treatment. Any biopsies performed according to local practice (e.g., not for cause) should also be recorded. In Part 2, biopsies performed for suspected rejection and other kidney disease related events will also be evaluated centrally by an independent Adjudication Committee.

Graft loss

The allograft will be presumed to be lost on the day the subject starts dialysis and is not able to subsequently be removed from dialysis. If the subject undergoes allograft nephrectomy prior to starting permanent dialysis, then the day of nephrectomy is the day of graft loss. The reason for graft loss will be recorded on the Graft Loss eCRF. This will be reported on the Study Completion eCRF and Treatment Phase Disposition eCRF with Graft Loss as the reason for study discontinuation and on the appropriate Dosage Administration Record eCRF(s) if death occurs while on randomized treatment. Graft loss is considered a SAE and should be reported on the Adverse Event eCRF (as serious) and the SAE reported to the local Novartis Drug Safety and Epidemiology Department local Novartis Drug Safety and Epidemiology (DS&E) Department within 24 hrs.

Death

In the event of subject death, the SAE leading to death should be reported to Novartis DS&E within 24 hrs. The events leading to the death should be entered on the Adverse Event eCRF and the death should be indicated on the appropriate Dosage Administration Record eCRF(s) (if death occurs while on randomized treatment), on the Study Completion eCRF and on the Treatment Phase Disposition eCRF.

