(6) First dose of CFZ533 will be administered intravenously pre- or intra-operatively and must be completed by the time of unclamping or up to 6 hours prior to the time of unclamping. Other study drugs (e.g., Tac, MMF, CS) should be started within 24 hours post-transplantation or according to local practice.

(7) First dose of basiliximab induction should be given within 2 hours prior to transplant surgery, or according to local practice. The second dose should be given on Day 4, or according to local practice.

(8) Local laboratory tests include: hematology, urinalysis, serum chemistries, renal function, and coagulation parameters.

(9) Obtained every 15 mins for 2 hrs after the start of the first CFZ533 IV infusion or time of SC injection.

(10) Negative test result must be available prior to randomization/enrollment.

(11) Blood collections and safety assessments should be taken pre-dose if the sampling falls on a dosing day.

(12) Blood draws for trough concentrations should be performed before the next dose is given. In addition, they should be performed locally as shown and additionally 5±2 days following each clinic visit in which doses are changed.

Corporate Confidential Information

(14) All serious adverse events, serious infections and pregnancies must be reported from informed consent until 3 months after his/her last dose of CFZ533 or 2 months

after EoS visit for patients on SoC treatment.

- (15) Induction therapy (e.g., basiliximab) and pre-transplant immunosuppression (if used) should be recorded on the Concomitant Medications CRF page under the Immunosuppressive category.
- (16) Prophylaxis for CMV, PCP, HBV, BK and oral candida to be considered per protocol [Section 5.5.8](#), and recorded on the Concomitant Medications CRF page if administered.
- (17) All patients are expected to continue in the study to Month 6 or 12 and complete the Month 6 or 12 Completion page, regardless of whether they are on or off study medication. If subjects discontinue study treatment, he/she should continue in the study on SOC per local practice and attend study visits to Month 6 or 12. Any permanent discontinuation of the randomized study regimen should be recorded on the appropriate DAR CRF pages. After discontinuation of study regimen, the immunosuppressive regimen prescribed should be recorded on the Concomitant Medications CRF under the Immunosuppressive category.

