3.1.2 All cohorts

Before any study-related evaluations are performed, the patient must give written informed consent. Once consent is obtained, pre-transplant screening and baseline assessments will occur to determine the patient's eligibility to participate in the study starting up to 28 days prior to transplantation. If the screening, baseline and study Day 1 visits occur in close proximity of each other (i.e., within a 12 hour timespan), certain repeated assessments may be omitted, as noted in the [Assessment schedule](#). Data collection from assessments performed at the clinical site as part of medical standard of care but prior ICF sign-off is acceptable in order to confirm patient eligibility for patients receiving an organ from a deceased donor, if assessed shortly before transplantation (i.e within 24h – matching the baseline window of Day -1 to Day 1) and in-line with inclusion and exclusion criteria.

Day 1 is defined as the day of randomization/enrollment and transplantation. This protocol defines 7 days to a week and 4 weeks (or 28 days) to a Study Month. For example, Week 2 is considered to start on Day 8 and Study Month 2 is considered to start on Week 5/Day 29. Randomization/enrollment should occur within 24 hours pre-transplant and drug administration will begin after randomization/enrollment. If CFZ533 is to be administered, the first dose of CFZ533 will be administered IV pre-transplant or intra-operatively, and must be completed by the time of unclamping. Other study drugs must be started within 24 hours post-transplant or according to local practice.

Patients who are randomized/enrolled but not transplanted will be replaced. All randomized/enrolled subjects are expected to continue in the study up to Month 6 (Part 1) or Month 12 (Part 2) regardless of being on or off randomized/assigned treatment. All subjects will be followed-up for safety (e.g., SAEs) for approximately three months after their last dose of CFZ533 or 2 months after the EoS visit for patients on SoC treatment.

[figure not shown]
Any treatment arm in which the rejection rate fulfills the *a priori* defined stopping rules (see [Section 5.5.10](#)) will be immediately discontinued at any time during the study.

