9.5 Analysis of secondary and exploratory variables

9.5.1 Efficacy

Other efficacy variables will be analyzed similarly to the primary efficacy endpoint, although without the non-inferiority test:

- tBPAR at Months 3, 6 and 12
- BPAR at Months 3, 6 and 12
- Graft loss at Months 6 and 12
- Death at Months 6 and 12
- Graft loss or death at Months 6 and 12
- Antibody mediated tBPAR at Month 12

For each of the efficacy endpoints (primary and secondary), simple event rate estimates (proportion of events) will be obtained and each CFZ533 treatment arm event rate will be compared with the control arm event rates using Z-statistics based on two-sided 95% confidence intervals for differences in event rates.

As supportive analyses, BPAR and tBPAR will also be analyzed using the adjudicated results.

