- AEs leading to discontinuation of a study drug by SOC and PT
- AEs leading to dose adjustment or interruptions of a study drug by SOC and PT
- Infections by type of infection (viral, bacterial, fungal, and others) and microorganism of infection
- Serious infections by type of infection and micro-organism of infection
- New onset diabetes mellitus
- AEs by standardized MedDRA query (SMQ) levels (broad and narrow search)
- AEs by standardized MedDRA query (SMQ) and preferred term (broad and narrow search)

In all tables about incidence rates of AEs / Infections, if a patient has multiple occurrences of an AE, this patient will be counted only once in the corresponding AE category. If a patient has multiple adverse events within a system organ class, s/he will be counted only once for that class. If a patient has multiple severity ratings for an AE while on treatment, s/he is only counted under the maximum rating. In the tables, only adverse events occurring at or after first drug intake are included.

Information pertaining to AEs noted during the study will be listed by patient, including the verbatim term given by the investigator, the PT and SOC given by the MedDRA dictionary, start and end date, causality, severity, and relationship to study drug as assessed by the investigator.

BK-polyoma viremia and nephropathy

The following variables will be summarized by treatment and listed by treatment group and patient:

Occurrence of BK-polyoma viremia any time post-transplantation

Occurrence of BK-polyoma virus nephropathy any time post-transplantation

The difference of the investigational regimens to the control regimen will be summarized by risk ratios and appropriate CIs.

Tuberculosis surveillance

Tuberculosis (TB) test data collected will be listed by patient and visit.

Pregnancy test

Pregnancy test results for all females will be listed by patient and visit.

Desirability of outcome ranking (DOOR)

Composite endpoint:

- a) Survived; without graft loss and without tBPAR
- b) Survived; without graft loss and with tBPAR
- c) Survived; with graft loss and without tBPAR
- d) Survived; with graft loss and with tBPAR
- e) death

Long term renal function:

- a) Normal creatinine; without BK and without tBPAR

- b) Normal creatinine; with BK and without tBPAR
- c) Normal creatinine; without BK and with tBPAR
- d) Normal creatinine; with BK and with tBPAR
- e) Elevated creatinine; without BK and without tBPAR

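### Protocol section 6.5.1 records graft loss as a reason for leaving the study, against the rule that all subjects are followed to Month 6 or 12; late deaths and serious events after graft loss may be missed once the SAE window closes.

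*Protocol*

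**What the plan says.** Protocol section 6.5.1, under graft loss, names the forms to be completed: "This will be reported on the Study Completion eCRF and Treatment Phase Disposition eCRF with Graft Loss as the reason for study discontinuation".

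The general follow-up rules point the other way:

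- Schedule footnote 17: "All patients are expected to continue in the study to Month 6 or 12 and complete the Month 6 or 12 Completion page", whether on or off study medication. Section 3.1.2 and the opening of section 6 say the same.
- Section 5.5.10: "Subjects who discontinue their study treatment regimen should NOT be considered withdrawn from the study UNLESS they withdraw their consent".
- Section 5.5.10 places graft loss in the list that begins "Possible reasons for study treatment discontinuation are". For pregnancy, the same section says expressly that the subject leaves both the medication and the study.
- Section 5.5.5 says that permanent dialysis or retransplantation ends study treatment. It asks for the Graft Loss and Adverse Event eCRFs and an SAE report, and does not mention the Study Completion page.

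The endpoints that depend on follow-up after graft loss include "Death at Months 6 and 12" (protocol section 9.5.1) and the SAP's DOOR composite (SAP section 7.1.2). The DOOR composite has ranks such as "c) Survived; with graft loss and without tBPAR" above the death rank.

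**The concern.** The two instructions cannot both be followed. A site that works from 6.5.1 could complete the Study Completion page at graft loss, after which no further study visit is due. Section 6.2 has adverse events recorded until the subject has completed the study, so early completion can also end adverse event recording. The exit would depend on an outcome, and arms that lose grafts at different rates would lose follow-up at different rates.

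Three outputs are at stake:

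- **Death as a separate endpoint.** Protocol section 9.5.1 analyses it as a simple proportion, so a death that is never collected counts as a non-event. SAP section 6.2.3 also treats death like time to tBPAR, where section 6.1.4 censors at last contact. Censoring at graft loss would then be informative.
- **Late serious events.** These include PTLD and PML, where two cases trigger the hold rule in protocol section 5.5.10 and SAP section 1.4.3.
- **The DOOR ranking.** A patient whose later death is not seen keeps a survived-with-graft-loss rank.

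**Working it through.** The plan states no figure on this point, so there is nothing to reproduce. The check has three parts.

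**1. Is 6.5.1 the outlier?** Footnote 17 and sections 3.1.2, 5.5.10 and 6 all require follow-up regardless of treatment status, and none excepts graft loss. Sections 5.5.5 and 5.5.10 link graft loss to stopping treatment. Only 6.5.1 has the words "with Graft Loss as the reason for study discontinuation". Its sentence also carries a condition about death occurring on randomized treatment, which belongs with the Death paragraph that follows. A drafting carry-over is plausible.

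**2. How much time would be uncovered?** Section 7.2 requires SAE reports until 3 months after the last CFZ533 dose, or 2 months after the end-of-study (EoS) visit on standard of care. The plan's study month is 28 days (section 3.1.2) and a calendar month is about 30.5 days. So 3 months is 84 to 91 days and 2 months is 56 to 61 days. Study completion is Day 364 (Appendix 1, Part 2).

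Uncovered days = max(0, 364 − anchor day − window length). The anchor is the last dose for CFZ533. For control it is the EoS visit, assumed here to fall on the day of graft loss.

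| Anchor day | CFZ533 window ends | CFZ533 uncovered days | Control window ends | Control uncovered days |
|---|---|---|---|---|
| 57 | 141–148 | 216–223 | 113–118 | 246–251 |
| 169 | 253–260 | 104–111 | 225–230 | 134–139 |
| 281 | 365–372 | 0 | 337–342 | 22–27 |
| 309 | 393–400 | 0 | 365–370 | 0 |

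Worked example for Day 57, CFZ533: 57 + 84 = 141 and 364 − 141 = 223; 57 + 91 = 148 and 364 − 148 = 216.

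The anchors behave differently. Early close-out does not move the CFZ533 window, which is tied to the last dose. It pulls the control window forward, because that window is tied to the EoS visit. In both arms it can end visits and adverse event recording. Capture could therefore differ by arm even at equal graft-loss rates.

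**3. How many patients?** Protocol section 1.1 cites 95% first-year graft survival. I take 5% graft loss as an assumption and show 2% and 10% around it, with 30 + 15 = 45 patients in Part 2.

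- Expected number at 5%: 0.05 × 45 = 2.25 (1.5 of 30 and 0.75 of 15).
- P(at least one of 45) = 1 − (1 − p)^45: 0.60 at 2%, 0.90 at 5%, 0.99 at 10%.
- One unrecorded death would shift an arm's death rate by 1/30 = 3.3 points (CFZ533) or 1/15 = 6.7 points (control). The documents do not give the probability that a death follows graft loss, falls outside the window and goes unrecorded, so this is the size of one case and not an expected bias.

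**The case against.** A reader might infer from 6.5.1 that all deaths and serious events after graft loss drop out of the comparison. The documents do not support that:

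- Section 6.5.1 names the forms but sets no day for completing them and cancels no visit. Early close-out is one literal reading, set against several explicit follow-up statements.
- SAEs, including fatal ones, stay reportable through the windows in section 7.2.
- Section 6 requires telephone contact, with the subject or an informant, about subject and graft status for treatment discontinuers who do not attend.
- Section 9.5.3 analyses all safety data collected, including data from after treatment discontinuation.

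A reader might also infer that the SAP misclassifies deaths after graft loss. It does not. SAP section 6.2.1 takes death from the Death eCRF without any condition on earlier graft loss. DOOR ranks a to d require survival, so a recorded death is already in the lowest rank.

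Finally, the treatment-discontinuation list in section 5.5.10 also contains death and loss to follow-up, so the list alone does not prove that graft loss ends treatment only.

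Most of this stands, and it limits the consequence. It does not remove the contradiction. The telephone provision is written for treatment discontinuers, not for subjects recorded as having left the study, and analysing all collected data cannot recover data that were never collected.

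**Conclusion.** The contradiction between section 6.5.1 and the follow-up rules is certain and must be reconciled. Its consequence is conditional: if sites apply 6.5.1 literally, deaths and serious events falling after the SAE window and before Month 12 may be missed, possibly unequally by arm. The gap is longest after early graft loss. It closes for a CFZ533 last dose at Day 281 or later, and for a control end-of-study visit at Day 309 or later.

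Few patients are likely to be involved: about 2 of 45 at the assumed 5%, and possibly none.

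The main efficacy results are not materially affected. The primary analysis counts on-treatment tBPAR, and treatment stops at permanent dialysis. Graft loss or death, and the composite of tBPAR, graft loss or death, already count the patient as a failure. A missing eGFR after graft loss is set to zero.

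The point is still worth correcting, because data not collected cannot be recovered at analysis and the correction is small.

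**What to change.** Reconcile the passages by amendment:

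1. In section 6.5.1, record graft loss as a reason for study treatment discontinuation only, in line with sections 5.5.5 and 5.5.10.
2. Complete the Study Completion eCRF at Month 6 (Part 1) or Month 12 (Part 2), or at actual withdrawal or death. Do not simply delete the form, since footnote 17 expects a completion page for every patient.
3. State that vital status and SAEs, including PTLD, malignancy and serious infection, are collected to Month 6 or 12 after graft loss, by telephone where visits are not possible, as section 6 already allows. This needs saying outright because the CFZ533 reporting window in section 7.2 is tied to the last dose and would not lengthen through items 1 and 2 alone.

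The SAP derivations of death and DOOR need no change beyond using this follow-up.

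The cost is a few lines of protocol text, a matching eCRF completion guideline, and some telephone contacts for about 2 patients.
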